### **B.6.17. EARLY SUBJECT WITHDRAWAL**

Although efforts will be made by Investigators and study staff to encourage eligible subjects to remain enrolled in the study, subjects may withdraw early from the study for a number of reasons, including but not limited to:

- Failure of SCS Trial Phase
- Subject request
- Investigator request
- Subject lost to follow-up
- Subject's death
- Adverse events (e.g., intolerable adverse event occurrence that forces subject to stop participation in the study)

If a subject is considering withdrawing from the study due to unsatisfactory effectiveness of DTM SCS programming, the Investigator will attempt to improve therapy during a study visit. When a subject is withdrawn early from the study, a Study Termination CRF will be completed describing the reason for discontinuation. Study staff will contact subjects to remind them about their scheduled visits and make sufficient efforts to locate a subject that is not responding to a contact call. If a subject has withdrawn consent for the study, or is lost to follow-up, the completion of this visit is not required. In situations where study withdrawal is due to a study-related adverse event, subjects will be followed until resolution of the adverse event or determination that the adverse event is not likely to change.

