## PROTOCOL SYNOPSIS

Study Title	A Post-Market, Observational Clinical Study to Evaluate the Effects of DTM™ SCS programming in treating Intractable Chronic Upper Limb Pain
Protocol Number	DTM-PROC-2020PM3
Study Device	Intellis™ neurostimulator, a Spinal Cord Stimulation (SCS) device system manufactured and commercialized by Medtronic (Minneapolis, MN)
Study Purpose	The purpose of this observational clinical study is to evaluate the effectiveness and to collect safety data of DTM™ SCS programming on subjects with chronic, unilateral or bilateral upper limb pain.
Study Design	This is a post-market, open-label, prospective, multi-center, observational study evaluating upper limb pain relief with the DTM SCS programming approach. Data at follow-up visits will be compared to baseline assessments collected at the beginning of the study.
Study Size	Up to 90 subjects may be consented and screened in clinical sites in the United States. This would allow approximately 45 subjects to be implanted.
Study Duration	The expected total duration of this study is approximately 26months. Enrollment of subjects is expected to last 20 months. Subjects that have received the permanent implant will be followed up for 12 months after their device has been activated. A subject will likely be committed to the study for about 14 months. This consists of Baseline assessments, up to 10 days of trial stimulation and 12months of treatment following implantation and activation of the device. All current subjects or those who have completed their 6-month visit will be offered to return for an additional 12-month visit. This would increase their commitment to the study to 14 months.
Study Objective	The primary objective of this study is to evaluate the effectiveness of DTM SCS programming as a treatment for reducing intractable chronic pain of the upper limbs.

	
The secondary objectives of this study are to further characterize the effectiveness of DTM SCS programming for the treatment of chronic pain of the upper limb and to collect safety data of DTM SCS programming.

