### **A.3. STUDY SIZE**

Approximately 45 subjects are expected to complete the 3-month endpoint of the study. Up to 90 subjects may be consented to participate at clinical sites in the United States. A sample size estimate is discussed further in section B.5.5 of this Clinical Study Plan.

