#### **B.5.4.1 SAMPLE SIZE RATIONALE**

There is no statistical hypothesis to be evaluated in this study. It is believed that approximately 45 subjects permanently implanted subjects will be sufficient to evaluate the effectiveness and to collect additional safety data of the DTM SCS programming in the target population at the primary endpoint.

Up to 90 subjects will be consented to participate in the eligibility screening process. Those who do not meet all the inclusion criteria and none of the exclusion criteria will be considered screen failures and will not move into the trialing phase. It is estimated that approximately 55 subjects will be trialed. Only subjects with a successful trial phase will be eligible to move into permanent implantation of the device.

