### **B.7.4. SECONDARY ENDPOINTS**

The following secondary endpoints will be evaluated:

- Change from Baseline in upper limb pain mean VAS score determined at the 3-month visit after device activation. This is calculated as: Change from Baseline in Upper Extremities Pain VAS = 3-Month Visit Pain VAS – Baseline Pain VAS. A negative result reflects a decrease in Pain VAS score, while a positive result reflects an increase in Pain VAS score.
- Change from Baseline in extend of disability as measured by mean Pain Disability Index (PDI), evaluated at 3 months after device activation.
- Frequency of treatment emergent adverse events.

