**Table 1. Schedule of Study Activities**

Activity	Pre-Trial Phase		Trial Phase		Permanent Phase					12 months visit (±31 days after activation)
	Enrollment	Baseline	Start Trial Phase	End Trial Phase (up to 10 days after trial starts)	Permanent Implant (up to 60 days after end of trial)	Device Activation (0-14 days after implant)	1-month visit (±15 days after activation)	3 months visit (±21 days after activation)	6 months visit (±31 days after activation)	
Informed Consent	X									X b)
Pain Intensity Evaluation (VAS)	X			X			X	X	X	X
Medication Use	X	X	X	X	X	X	X	X	X	X
Medical/Surgical History	X	X								
Eligibility Criteria Evaluation	X									
Pain Disability Questionnaire		X							X	X
AP/Lateral x-ray imaging			X	[X]	X	[X]	[X]	X	[X]	[X]
Paresthesia Questionnaire								X	X	X
Patient Global Impression of Change								X	X	X
Subject Satisfaction								X	X	X
Adverse Event Monitoring		X	X	X	X	X	X	X	X	X
Device Programming			X			X	[X]	[X]	[X]	[X]
Device Programming Log				[X]			[X]	[X]	[X]	[X]
Study Completion				X a)				[X] c	[X] c	X c

[X] Optional activity.

a) For subjects that do not have a successful Trial Phase.

b) Some subjects may need to be reconsented to complete these visits.

c) Some subjects were originally consented to complete the study at the 3 or 6 month visit and may not consent for additional visit.

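### B.6.17 refers to a visit at early withdrawal that is nowhere defined, so implanted subjects who leave before month 3 owe no exit pain, disability, PGIC or satisfaction rating

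*Combined protocol and SAP*

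**What the plan says.** B.6.17 (Early Subject Withdrawal) lists reasons for leaving, among them subject request, adverse events and loss to follow-up. If a subject thinks of leaving because relief is unsatisfactory, the investigator is to try to improve therapy at a study visit. On withdrawal, "a Study Termination CRF will be completed describing the reason for discontinuation". The section then adds: "If a subject has withdrawn consent for the study, or is lost to follow-up, the completion of this visit is not required". No closing visit has been introduced at that point.

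Other sections that bear on an early leaver:

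- **Table 1:** no early-withdrawal column. Trial failures do have an exit point, at the end of the Trial Phase, where VAS is also taken.
- **B.6.9 (Unscheduled Visits):** adverse events, medication changes and programming, with no rating listed.
- **B.6.16 (Device Explant):** return of hardware, with no rating listed.
- **B.6.11 (month 1):** VAS, but no disability, PGIC or satisfaction rating. B.6.12 and B.8.1 start those after-treatment questionnaires at month 3.
- **B.6.15:** allows remote data collection, but holds back mailed questionnaires from non-compliant subjects, with switching the device off as one example.
- **B.7.4:** the first secondary endpoint is "Change from Baseline in upper limb pain mean VAS score determined at the 3-month visit after device activation", and the disability change is also fixed at month 3.
- **B.7.1 and B.9.2:** the analysis population is implanted subjects who finish the study without disqualifying deviations. The analysis is descriptive and has no missing-data rule.

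**The concern.** Excusing two groups from a visit implies that others attend it, but a site reading B.6.17 cannot tell which visit is meant or what to collect. The gap falls on implanted subjects who leave before month 3. If they leave after month 1, the last pain rating the plan requires is the month-1 VAS. If they leave sooner, no rating after activation is required. In neither case is any disability, PGIC or satisfaction value due after treatment. This holds even where B.6.17 itself brings the subject to a visit because relief is poor.

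The study is open-label and single-arm, so no comparator would reveal outcome-related loss. B.6.17 expects some subjects to consider leaving for lack of effect, so such loss is foreseeable. The 3-month mean changes in VAS and disability would then describe those who stayed.

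**Working it through.** **1. The plan's own numbers.** The Synopsis says of the number consented: "This would allow approximately 45 subjects to be implanted". A.3 says: "Approximately 45 subjects are expected to complete the 3-month endpoint of the study". B.5.4.1 adds: "It is estimated that approximately 55 subjects will be trialed". The implied trial-to-implant rate is 45/55 = 81.8%. The implied loss between implant and month 3 is 45 - 45 = 0. The figure of 45 cannot be derived further, since B.5.4.1 states: "There is no statistical hypothesis to be evaluated in this study". No effect size, SD or attrition rate is given.

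**2. What a leaver owes under the plan as written.**

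| Time of leaving | VAS after activation | Disability, PGIC, satisfaction after treatment |
|---|---|---|
| Before the month-1 visit | none required | none required |
| Between months 1 and 3 | month 1 only | none required |
| After the month-3 visit | months 1 and 3 | month 3 |

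The last row follows the text of B.6.12 and B.8.1. Table 1 as extracted shows no month-3 mark for the disability questionnaire, which may be an extraction fault. An end-of-trial VAS also exists, but it predates the implant.

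**3. Size of the effect on the mean VAS change.** The 45 comes from the plan; everything else is assumed. Let w be the number of leavers before month 3, C the completer mean change and L the leaver mean change.

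Mean over all implanted = [(45 - w) × C + w × L] / 45

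Overstatement = w × (|C| - |L|) / 45

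With C = -4.5 cm and L = -1.0 cm:

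- w = 2: (43 × -4.5 + 2 × -1.0)/45 = -195.5/45 = -4.34 cm; overstatement 0.16 cm
- w = 5: (40 × -4.5 + 5 × -1.0)/45 = -185/45 = -4.11 cm; overstatement 0.39 cm
- w = 8: (37 × -4.5 + 8 × -1.0)/45 = -174.5/45 = -3.88 cm; overstatement 0.62 cm

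These are losses of 2/45 = 4.4%, 5/45 = 11.1% and 8/45 = 17.8%.

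**4. Range.** Let C run from -3.5 to -5.5 cm and L be 0 or -1 cm. The smallest gap is 3.5 - 1 = 2.5 cm and the largest is 5.5 - 0 = 5.5 cm.

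| w | Smallest: 2.5w/45 | Largest: 5.5w/45 |
|---|---|---|
| 2 | 0.11 cm | 0.24 cm |
| 5 | 0.28 cm | 0.61 cm |
| 9 | 0.50 cm | 1.10 cm |

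The direction depends only on leavers improving less than completers. If they improve equally, the overstatement is zero.

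**5. Would collection alone change the reported mean?** Not under B.7.1. A subject who leaves before month 3 has not completed the study, so an exit rating would stay outside the analysis population. The visit and the rule for using its data have to be written together.

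**The case against.** The strongest reply is that B.6.17 never mentions a closing visit. The preceding sentence concerns reminders about scheduled visits and tracing subjects who do not respond, so *this visit* could mean the next scheduled one, with its Table 1 assessments. That reading is possible, and the plan cannot be said to promise every other leaver an exit visit. It does not settle the matter: the text does not choose between readings, and a subject already withdrawn has no obvious next scheduled visit.

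A reader might infer that leavers give no rating at all and that the worst results are lost for good. The documents do not support this. They show that ratings are not required, not that none will be taken. A withdrawal may coincide with a scheduled visit, a month-1 VAS will often exist, and anyone leaving after the month-3 visit already has the 3-month VAS. The study flowchart and the case report forms cannot be read here and may hold more. Nor need every leaver be a failure, since B.6.17 lists other reasons.

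A reader might also infer that no analysis could help. Leavers could be counted as non-responders for the primary endpoint without any exit rating, and the mean VAS change could be bounded using month-1 or baseline values. For disability, however, only baseline would be available.

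It is also fair that the missing visit is not the sole cause: B.7.1 and the silence of B.9.2 on missing data contribute. Finally, the study tests no hypothesis, so no formal decision changes. These points limit the concern but leave the gap in place.

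**Conclusion.** The point holds as a gap in required data collection. B.6.17 relies on a visit that no section or Table 1 column defines. Implanted subjects who leave before month 3 are not required to give any pain rating after month 1, or any disability, PGIC or satisfaction rating after treatment. The 3-month mean changes are then likely to flatter the therapy if leavers do worse.

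The illustrated size is 0.2 to 0.6 cm on the 10 cm VAS for 2 to 8 leavers of 45, and 0.1 to 1.1 cm over the wider range for 2 to 9 leavers. Only the 45 is the plan's figure, so these are illustrations and not estimates. The effect shown is on a secondary endpoint, and the primary endpoint is not part of this finding. The change is worth making because it is cheap and the loss is foreseeable.

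**What to change.** - **Define the visit.** In B.6.17, name an early-withdrawal assessment for implanted subjects and add a Table 1 column: VAS, disability questionnaire, PGIC, satisfaction, medication use and programming log. Allow it in clinic or by the remote routes in B.6.15, and say that the hold on mailed questionnaires does not apply to it. Waive it only for withdrawn consent, loss to follow-up or death.
- **Record stimulation status.** Note whether stimulation was on or off at the rating. This sets no rule on when to stop stimulation or explant.
- **State how the data are used.** If the assessment falls within the 3-month window (±21 days), use it as the 3-month value, and say in B.7.1 that the completion requirement does not remove such a subject from the 3-month summaries. Otherwise, report exit VAS and disability change in a separate row beside the completers' means.
- **Add a sensitivity mean** over all implanted subjects using the last available rating. The separate row shows the leavers but does not move the completer mean; this does. State in advance what is used when no rating after activation exists. The end-of-trial VAS would flatter, since implantation requires at least a 40% reduction at that point. Zero change from baseline is a simple choice.

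The cost is one table column, a short paragraph and one extra set of existing forms for a few subjects. The reported mean change may come out slightly less favourable.

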### **B.6.6. END OF TRIAL ASSESSMENT**

At the end of the Trial Phase, subjects will be assessed for pain intensity under optimal therapy parameters. Anterior-posterior (AP) and lateral X-ray imaging may be done at the end of the Trial Phase. The subject will be assessed for study-related adverse events and medication usage.

Subjects who have a "successful Trial Phase" (defined as a 40% or greater pain reduction from Baseline in the upper limbs pain and the subject would like to move forward to the implant phase) will proceed to permanent implantation of a SCS system to evaluate DTM SCS programming. Permanent implantation of the Intellis™ SCS system will be scheduled. A threshold of 40% for the Trial Phase was predetermined as the minimum pain reduction that warrants consideration of a permanent implant and an opportunity to achieve a 50% pain reduction as defined in the Individual Subject Success criterion (see Section B.7.3).

Subjects who did not achieve 40% or greater pain reduction in upper limb and do not receive permanent implantation will exit the study after being followed up for two weeks after removal of the leads to assess study-related adverse events.

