### **B.6.16. DEVICE EXPLANT**

At any time during the study, a subject may elect to withdraw from the study and have the SCS device system explanted. Additionally, an Investigator may elect to explant a device due to an adverse event.

The Investigator must follow the appropriate guidelines set forth by the manufacturer of the device for returning the explanted device and/or lead(s) as well as the accessories (charger, patient remote control).

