### **B.6.19. STUDY SUSPENSION AND TERMINATION**

Subjects will be considered to have completed all study requirements following the completion of the follow up visit 3 Months after Device Activation. All subjects who remain implanted at the time of Study Completion will be offered to return for an additional visit 6-months after device activation.

Each clinical site will be considered to have completed study requirements at the end of the required monitored close out visit. The study will be considered terminated when all of the requirements of this Clinical Study Plan have been fulfilled, all close out visits have been completed and all Sponsor and Investigator reports have been issued and reported to the IRB.

The Sponsor, the Investigators, or the IRB(s) may suspend or terminate the study early at any time. If the study is suspended or terminated prematurely, all subjects that are still enrolled will be terminated from the study. A Study Completion CRF will be completed noting that the study has been terminated. If there is an ongoing study-related adverse event, the subject will be followed until resolution of the adverse event or determination that the adverse event is not likely to change.

Subsequent follow-up of the subjects after study completion will be the responsibility of the subject's personal physician.

The Sponsor reserves the right to terminate the study but intends only to exercise this right for reasons related to the protection of subjects or valid scientific or business reasons. The Sponsor will notify Investigators and IRBs in writing in the event of study termination.

The Sponsor reserves the right to stop the enrollment of subjects at any clinical site at any time after the clinical site initiation. Possible reasons for suspending or terminating a clinical site may include, but are not limited to

- Non-compliance by Investigator
- Failure to obtain proper written informed consent
- Repeated failure to complete or submit CRFs in a timely manner
- Failure to report study-related serious adverse events (SAEs) or unanticipated adverse device events (UADEs) to the Sponsor within 48 hours of knowledge of the event and to reviewing IRB in accordance with its policies

- Repeated failure to comply with clearance of queries generated during monitoring of the study
- Inactivity

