***System Revision Risk:***

The Intellis Neurostimulator may require replacement in 9 years or earlier, regardless of the number of times the neurostimulator is recharged. It is possible that the system will need to be revised (explanted, replaced, or repositioned) earlier than 9 years. Possible reasons for revision/explant may include infection, malfunction, and migration of the system components. The risks associated with system revision are equivalent to the commercially available systems.

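### Early withdrawal follow-up depends on the reason for leaving, and no adverse event collection is set after explant, so some device and explant harms may go unrecorded

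*Combined protocol and SAP*

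**What the plan says.** Section B.6.16 (Device Explant) gives two routes to explant. In the first, "At any time during the study, a subject may elect to withdraw from the study and have the SCS device system explanted". In the second, "Additionally, an Investigator may elect to explant a device due to an adverse event". The only procedure it then sets is return of the hardware. It gives no visit, call or event collection period, and it does not place explant before or after study exit.

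Section B.6.17 (Early Subject Withdrawal) has a Study Termination CRF completed at withdrawal and limits later follow-up to one situation: "In situations where study withdrawal is due to a study-related adverse event, subjects will be followed until resolution of the adverse event", or until that event is judged unlikely to change. It also says "If a subject has withdrawn consent for the study, or is lost to follow-up, the completion of this visit is not required", without saying which visit is meant.

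Other exits are treated differently. Under B.6.6, subjects who fail the trial and are not implanted are "followed up for two weeks after removal of the leads to assess study-related adverse events". Under B.6.19, if the study is stopped early, "If there is an ongoing study-related adverse event, the subject will be followed until resolution", whatever the reason for stopping. Sections B.6.12 to B.6.14 and B.6.18 apply the same ongoing-event rule at the scheduled visits and when the 12-month visit is declined.

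Section B.8.3.2 captures adverse events from enrollment to study completion and does not define that end for a withdrawn subject. Section B.7.4 makes the frequency of treatment-emergent events a secondary endpoint. Section B.7.1 defines a single analysis population, implanted subjects who complete the study. Section C.1 (System Revision Risk) foresees explant: "Possible reasons for revision/explant may include infection, malfunction, and migration of the system components".

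**The concern.** There are two gaps, and they lose different information.

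The first is in B.6.17. An implanted subject who leaves for poor relief while a study-related event is unresolved, for example pain at the neurostimulator site, is not followed, because that event was not the reason for leaving. A completer with the same event is followed. The event itself will already have been recorded. What is lost is its outcome, including any worsening, although B.8.3.2 asks for resolution to be documented for every study-related event.

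The second is in B.6.16. A new event caused by explant surgery may begin after the subject has left, when no rule requires anyone to ask about it. Here the event itself may be missing from the count. Even a subject who withdraws because of a study-related event is followed only for that event, so new explant harms need not be sought.

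Collecting safety data is a stated secondary objective (B.2). Omissions of this kind can only lower the event count, and they would fall among subjects who gave up the therapy.

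**Working it through.** The plan states no hypothesis, explant rate or explant complication rate, so there is no figure of its own to reproduce. The check is mainly a comparison of the rules.

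| How the subject leaves | Section | What triggers follow-up | New events after hardware removal sought? |
|---|---|---|---|
| Failed trial, not implanted | B.6.6 | Lead removal itself | Yes, for two weeks |
| 3-, 6- or 12-month visit | B.6.12 to B.6.14 | Any ongoing study-related event | Not applicable |
| Declines 12-month visit | B.6.18 | Any ongoing study-related event | Not applicable |
| Study stopped early | B.6.19 | Any ongoing study-related event | Not stated |
| Individual early withdrawal | B.6.17 | Only an event that caused the withdrawal | Not stated |
| Explant | B.6.16 | None stated | Not stated |

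Applied to particular implanted subjects:

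1. Withdraws for poor relief with a study-related event ongoing: no follow-up required under B.6.17.
2. Withdraws for poor relief, exits, is then explanted and develops an infection: no rule requires collection.
3. As in 2, but explanted before exit: B.8.3.2 applies until exit. Nothing ties the exit date to the explant date, so the observed interval could be very short.
4. Withdraws because of a study-related event and is explanted: followed for that event only.
5. Explanted by the investigator for an adverse event and stays enrolled: B.8.3.2 capture continues.

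The gap is clear in cases 1 and 2 and partial in cases 3 and 4. It is absent in case 5.

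**Illustration of size.** From the documents: n = 45 implanted (synopsis and B.5.4.1). Assumed, with no support in the documents: explant proportion e from 2% to 15%, and complication rate per explant a from 5% to 20%.

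- Expected explants = n × e: 45 × 0.02 = 0.9, up to 45 × 0.15 = 6.75.
- Expected explant complications = n × e × a: 45 × 0.02 × 0.05 = 0.045, up to 45 × 0.15 × 0.20 = 1.35.
- Chance of at least one = 1 − (1 − e × a)^45: 1 − 0.999^45 = 0.044, up to 1 − 0.97^45 = 0.746.
- In the narrower range e = 5% to 10%: 2.25 to 4.5 explants, 0.11 to 0.9 complications, and a chance of at least one of 0.107 to 0.597.

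These are upper limits on what could be missed under each assumption, because they treat every explant as uncovered. Cases 3 to 5 show that some are not. One additional subject with an event would move an implanted-subject rate by 1/45 = 2.2 percentage points, but only if the denominator is all implanted subjects and that subject had no other counted event.

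**The case against.** A reader might infer that every subject who withdraws and is explanted leaves observation, so that explant harms are certain to be uncounted and the safety result is biased downward. The documents do not support that. Section B.6.16 does not say that exit comes first, and if explant comes first, B.8.3.2 covers events up to exit. Subjects who withdraw because of a study-related event remain under follow-up for it, and several reasons for explant listed in C.1 could be such events. Section B.6.9 allows unscheduled visits for possible study-related events while the study runs. The duty in E.3 to report serious events within 48 hours runs from knowledge of the event and states no cutoff at subject exit. All of this stands, and it limits the claim to events that may go unrecorded.

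It can also be said that the sections differ without contradicting one another, since each governs a different kind of exit. That is correct: this is an asymmetry. It still matters, because B.6.17 applied literally drops a subject whom the other sections would keep. The lack of an explant or withdrawal column in Table 1 adds little, since unscheduled visits have no column either.

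The documents do not compare the risk of explant with that of trial-lead removal, and the point does not need that comparison. Two weeks is the plan's own precedent, but nothing shows that it is the right length after explant.

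The strongest objection is that better collection might not change the report. Early withdrawals fall outside the completers-only population of B.7.1, and the treatment-emergent window is undefined. This also stands, and it is a reason to extend the fix to the analysis population.

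**Conclusion.** The point holds for implanted subjects who withdraw early for a reason other than a study-related adverse event. An ongoing study-related event in such a subject need not be followed, although the plan follows it at completion and at study termination. New harms from explant surgery may also go unrecorded, because the order of explant and exit is unstated and no collection after explant is set. For subjects who withdraw because of an event, only that second gap applies.

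The number affected is small and cannot be fixed from the documents. The range of 0.05 to 1.35 expected explant complications rests entirely on assumed rates and overstates what would be missed. The study is descriptive and the primary endpoint is not touched. The case for change rests on the unequal rules and on how little the repair costs. It does not depend on a demonstrated bias.

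**What to change.** 1. In B.6.17, make the trigger for continued follow-up the presence of an ongoing study-related adverse event at withdrawal, whatever the reason for leaving, for subjects who have not withdrawn consent. This matches B.6.18 and B.6.19. Name the visit that the section refers to.
2. In B.6.16, state that for adverse event purposes explant takes place before study exit, and that study-related events are collected for a stated period afterwards. The sponsor should set the length and reconcile it with B.6.6. Phone collection is already permitted in B.6.15. File the Study Termination CRF after that contact.
3. In B.7.1 or B.9.2, state that safety is summarised in all trialed or implanted subjects and not only in completers, so that these events enter the frequency reported under B.7.4.

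The cost is amendment wording and about one call per explanted subject. Events in subjects who withdraw consent or are lost to follow-up would remain largely uncollectable, and the report should give their number.
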